#### Step 2: Combination of events:

Overlapping/consecutive events are defined as events of the same subject with the same preferred term which have at least 1 day overlap or for which the start date of an event is 1 day after the end date of the preceding event. Overlapping/consecutive events may be combined into one AE or not, according to the following rules:

- 1) If overlapping/consecutive events start in one of the following periods - Screening or post dose extension (i.e. non-active periods) - followed by an AE in - post-dose period (active period) - they are allocated to their respective periods and are considered as separate events.
- 2) In case overlapping/consecutive events start within a single period, they are considered as one and the same AE. The individual events which contribute to this AE are retained as individual

records in the ADaM database but are assigned the same onset, period, and total duration. All related attributes to the AE/phase/period should also be consistent with the new event.

3) In case overlapping/consecutive events start in both an active period followed by a non-active period, they are allocated to the active period only and are considered as one and the same AE. The individual events which contribute to this AE are retained as individual records in the ADaM database but are assigned the same onset, treatment period, and total duration. All related attributes to the AE/phase/period should also be consistent with the new event.

4) In case an active period is followed by another active period, and the overlapping/consecutive events start in both periods, they are allocated to their respective period and are considered as separate AEs. The same rule applies for 2 non-active periods.

Remarks:

1. Events can only be combined into one and the same AE if their start and stop dates are known.
2. In case the completely missing end date is imputed (for period allocation), this date is also considered as a complete date.
3. Time is not considered when determining overlap of events.

#### **5.1.4. Handling of Missing Data for Adverse Events**

Missing data will not be imputed. Subjects who do not report an event will be considered as subjects without an event. The analysis of the solicited AEs will include only documented safety data (i.e. in case severity is missing it is not considered an event).

#### **5.1.5. Solicited Local (Injection Site) Reactions**

The analysis of local solicited adverse events will include:

1. Pain/Tenderness
2. Erythema
3. Induration/Swelling

#### **5.1.6. Solicited Systemic Adverse Events**

The analysis of systemic solicited adverse events will include:

1. Fever (defined as body temperature of 38.0°C or higher)
2. Headache
3. Fatigue
4. Myalgia
5. Nausea
6. Chills

## 5.2. Clinical Laboratory Tests

Any clinically relevant lab value measured from signing of the ICF onwards must be recorded on the adverse event page of the CRF and are analyzed as AE. The data will be summarized by the type of laboratory test.

In case a laboratory test result is *censored* (no numeric value is available, but only a verbatim term) then a numeric value will be imputed by a value preceding or exceeding the cut-off value with one unit. (<x: subtract 1 unit from x, >x: add 1 unit to x)

*Toxicity grades* will be determined according to the DAIDS Grading list (see also [APPENDIX 1](#)). In case no toxicity grades are defined for a test, the abnormalities (above/below normal range) will be used. In determining toxicity grades, the following rules are applied:

- worst grades/abnormalities are determined over the whole observational period for each trial phase separately, including all post-baseline measurements of that phase.
- The abnormalities ‘abnormally low’ and ‘abnormally high’ are considered equally important, i.e. if a subject has as well an abnormally low as an abnormally high value post-baseline, both abnormalities are shown in the tables. (This means that the sum of the percentages can be more than 100%)
- Note: as the grading scale for some parameters in the grading table has some gaps (zones where no toxicity grade definition exists), laboratory results falling in these zones will be allocated to the adjacent worst-case grade.
- If a lab value falls within the grading as specified in the grading table but also within the (local) lab normal limits, the value is considered as normal

Definition emergent: An abnormality (toxicity grade or abnormality based on normal ranges) will be considered emergent in a particular phase if it is worse than the baseline (baseline = prior very first vaccination). If the baseline is missing, the abnormality is always considered as emergent. A shift from ‘abnormally low’ at baseline to ‘abnormally high’ post baseline (or vice versa) is also emergent.

### 5.2.1. Analysis methodology

Laboratory data will be analyzed based on the full analysis set. Unless specified otherwise, percentages are calculated versus the number of subjects in the analysis set with non-missing data for the parameter, period (if applicable) and treatment group under evaluation.

Tabulations of the worst graded abnormalities per period following vaccination will be provided. Grade 3 and 4 toxicities developed following vaccination will be listed. Tabulations of the worst emerging abnormalities (below/ above) will be performed for tests that have no grading.

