4.1. Inclusion Criteria for the Main Study

Each potential subject must satisfy all of the following criteria to be enrolled in the study.

1. Each subject must sign an informed consent form (ICF) indicating that he or she understands the purpose of and procedures required for the study and is voluntarily willing to participate in the study.
2. Subjects are ≥ 18 to ≤ 50 years old on the day of signing the ICF.
3. Subject must be healthy on the basis of physical examination, medical history, and vital signs measurement performed at screening.
4. Subjects must meet following laboratory criteria prior to randomization*:
 - a) Hemoglobin: Women ≥ 10.5 g/dL; Men ≥ 11.0 g/dL
 - b) White cell count: 2,500 to 11,000 cells/mm³, inclusive
 - c) Absolute neutrophil count: $>1,000$ cells/mm³
 - d) Platelets: 125,000 to 450,000 per mm³, inclusive
 - e) Urinalysis: protein $<1+$, blood $<1+$ (men) and $<2+$ (women), and glucose negative
 - f) Alanine aminotransferase/aspartate aminotransferase: $<1.25\times$ upper limit of normal (ULN)
 - g) Creatinine: $<1.1\times$ ULN

*If laboratory screening tests are out of range, repeat of screening tests is permitted once.

5. Subjects are negative for HIV infection at screening^a.
6. All female subjects of childbearing potential must have a negative serum (β -human chorionic gonadotropin [β -hCG]) at the screening visit, and a negative urine pregnancy test pre-dose on Day 1^b.
7. Contraceptive requirements for heterosexually active female subjects (from 28 days prior first vaccination up until 3 months after last vaccination)^c:
 - a) If not of childbearing potential: postmenopausal (>45 years of age with amenorrhea for at least 2 years, or any age with amenorrhea for at least 6 months and a serum follicle stimulating hormone [FSH] level >40 IU/L) or surgically sterile: no additional contraception required.
 - b) If of child-bearing potential, but has a vasectomized partner (after vasectomy: sperm count below the limit of detection if procedure occurred <1 year ago^d): no additional contraception required.
 - c) If of child-bearing potential, but has a non-vasectomized partner, or partner had a positive sperm count after a vasectomy procedure of <1 year ago^d, should be practicing an acceptable effective method of contraception. Acceptable methods for this study include:
 - Hormonal contraception,
 - Intrauterine device (IUD),
 - Intrauterine hormone-releasing system (IUS),
 - Male or female condom with or without spermicide,

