11.5. Safety Analyses

No formal statistical testing of safety data is planned. Safety data will be analyzed descriptively.

Baseline for all safety parameters will be defined as the last evaluation done before the first dose of study vaccine.

AEs

The verbatim terms used in the CRF by investigators to identify AEs will be coded using the Medical Dictionary for Regulatory Activities (MedDRA). All reported AEs and events-related diary information (solicited local at injection site and systemic, and unsolicited) with onset within 28 days after each vaccination (ie, treatment-emergent AEs, and AEs that have worsened since baseline) will be included in the analysis. For each AE, the number and percentage of subjects who experience at least one occurrence of the given event will be summarized by group and/or by vaccine.

Summaries, listings, datasets, or subject narratives may be provided, as appropriate, for those subjects who die, who discontinue treatment due to an AE, or who experience a severe AE, an SAE, or an AESI.

Summaries and listings may be provided separately for AEs with onset outside the above defined timeframe and that were reported pre-dose at the moment of subsequent vaccinations.

Solicited local (at injection site) and systemic AEs will be summarized descriptively. The overall frequencies per vaccine group as well as frequencies according to severity and duration will be calculated for solicited AEs. In addition, the number and percentages of subjects with at least one solicited local (at injection site) or systemic AE will be presented. Frequencies of solicited and unsolicited AEs, separately for all and vaccination-related only, will be presented by System Organ Class and preferred term.

Clinical Laboratory Tests

Laboratory data will be summarized by type of laboratory test. Laboratory abnormalities will be determined according to a modified version of the DAIDS grading table, Version 2.0 ([Attachment 1](#)), and in accordance with the normal ranges of the clinical laboratory. Laboratory abnormalities will be tabulated per treatment group and/or per vaccine.

Vital Signs

The percentage of subjects with values beyond pre-specified limits (see [Attachment 1](#)) will be summarized.

Physical Examination

Physical examination findings will not be tabulated separately. Clinically relevant findings will be reported as AE and will be tabulated and listed as AEs. BMI will be calculated using the recording of height at screening.

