**APPENDIX 1: LABORATORY, VITAL SIGNS AND ABNORMALITY GRADINGS**

PARAMETER	LABORATORY a			
	GRADE 1 MILD	GRADE 2 MODERATE	GRADE 3 SEVERE	GRADE 4 POTENTIALLY LIFE-THREATENING
HEMATOLOGY				
Absolute Neutrophil Count (ANC) (cells/L) c	800 x 10  – 1.000 x 10 	0.600 x 10  – 0.799 x 10 	0.400 x 10  – 0.599 x 10 	<0.400 x 10 
Hemoglobin (Hgb) (HIV NEGATIVE ONLY)				
Male	10.0 – 10.9 g/dL	9.0 – 9.9 g/dL	7.0 – 8.9 g/dL	<7.0 g/dL
Female	9.5 – 10.4 g/dL	9.4 – 8.5 g/dL	8.4 – 6.5 g/dL	<6.5 g/dL
Platelets, decreased b	100.000 x 10  – 124.999 x 10  /L	50.000 x 10  – 99.999 x 10  /L	25.000 x 10  – 49.999 x 10  /L	<25.000 x 10  /L
WBC, decreased b	2.000 x 10  – 2.500 x 10  /L	1.500 x 10  – 1.999 x 10  /L	1.000 x 10  – 1.499 x 10  /L	<1.000 x 10  /L
CHEMISTRIES				
ALT (SGPT)	1.25 – 2.5 x ULN	2.6 – 5.0 x ULN	5.1 – 10.0 x ULN	>10.0 x ULN
AST (SGOT)	1.25 – 2.5 x ULN	2.6 – 5.0 x ULN	5.1 – 10.0 x ULN	>10.0 x ULN
Creatinine	1.1 – 1.3 x ULN	1.4 – 1.8 x ULN	1.9 – 3.4 x ULN	≥ 3.5 x ULN
URINALYSIS				
Hematuria	6-9 RBC per high power field	≥10 RBC per high power field	Gross, with or without clots or with RBC casts	Transfusion indicated
Proteinuria, random collection	1+	2+	3+ or higher	NA

aThis list is restricted to the laboratory parameters collected in this study for which a DAIDS 2.0 grading is available. Only ranges applicable for adults are reported. For a complete list refer to the CTP appendix 1

bThe decrease is a decrease from baseline

cIf ANC is not available the values will be derived by from the ratio Neutrophils/Leucocytes

VITAL SIGNS a					
PARAMETER	UNIT	GRADE 1	GRADE 2	GRADE 3	GRADE 4
Temperature	°C	≥38.0 - ≤38.5	≥38.6 - ≤39.2	≥39.3 - ≤39.9	≥40.0
Hypertension					
Systolic Blood Pressure	mmHg	≥140 - ≤159	≥160 - ≤179	≥180	NA
Diastolic Blood Pressure	mmHg	≥90 - ≤99	≥100 - ≤109	≥110	NA
Hypotension	mmHg	NA	NA	NA	NA
Pulse rate					
Tachycardia	bpm	≥101-≤115	≥116 - <130	>130	NA
Bradycardia	bpm	≥50 - ≤54	≥45 - ≤49	<45	NA

aDAIDS 2.0 grading, see also CTP appendix 1

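### Read literally, the SAP puts high WBC, neutrophil and platelet counts after vaccination in no laboratory abnormality table, because normal-range flags are assigned by test and not by direction

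*SAP*

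**What the plan says.** SAP 5.2 grades laboratory results on the DAIDS scale and sets a fallback: "In case no toxicity grades are defined for a test, the abnormalities (above/below normal range) will be used". SAP 5.2.1 carries this into the outputs. For graded tests: "Tabulations of the worst graded abnormalities per period following vaccination will be provided". For the rest: "Tabulations of the worst emerging abnormalities (below/ above) will be performed for tests that have no grading". The only laboratory listing that 5.2.1 specifies is of Grade 3 and 4 toxicities.

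SAP Appendix 1 has one row each for the three counts at issue. Two are named for a fall, "WBC, decreased" and "Platelets, decreased". The ANC row names no direction, but its grades run downwards to Grade 4 below 0.400 x 10⁹/L. Protocol Attachment 1 agrees: ANC is graded as low, platelets and WBC as decreased. Neither table has a row for a high count.

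Protocol 11.5 says that abnormalities are determined by the modified DAIDS table "and in accordance with the normal ranges of the clinical laboratory", and are then tabulated. It does not confine the normal ranges to ungraded tests.

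**The concern.** Whether a normal-range flag is used depends on whether the test has any grade, not on whether it has one in the direction of the observed value. A test graded on one side only therefore loses the other side from the abnormality tables.

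Safety is a primary objective, and this is the first-in-human evaluation of Ad26.Mos4.HIV. The protocol attends to the high side of two of these counts at entry: "White cell count: 2,500 to 11,000 cells/mm³, inclusive" and "Platelets: 125,000 to 450,000 per mm³, inclusive" (Protocol 4.1; the ANC criterion there has no upper limit). If a regimen raised WBC, neutrophils or platelets after vaccination, the tables meant to show laboratory abnormalities by regimen and period would not show it.

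The output would also be uneven. Hematocrit and red cell count are in the hematology panel (Protocol 9.3) but absent from Appendix 1, so they would be tabulated in both directions, while WBC, ANC and platelets would be tabulated in one.

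**Working it through.** The plan states no figure on this point, so there is none to reproduce. The check applies the written rule to values above an upper limit. All counts are in 10⁹/L; 1,000 cells/mm³ equals 1 x 10⁹/L.

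**Inputs**

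| Test | Highest value with any grade, T (SAP Appendix 1) | Upper limit used, U | Source of U |
|---|---|---|---|
| WBC | 2.5 | 11.0 | Protocol 4.1 entry limit, standing in for the laboratory limit |
| Platelets | 124.999 | 450 | Protocol 4.1 entry limit, standing in for the laboratory limit |
| ANC | 1.000 | 7.5 | Assumption; the documents give no upper limit |

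The printed lower bound of ANC Grade 1 in Appendix 1 is 800 x 10⁹. It is out of line with the other cells and with Attachment 1, so it is read as 0.800.

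**Rule as written.** A value v enters an abnormality table if

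- it has a grade, which for these tests means v ≤ T; or
- the test has no grading and v is outside the normal range.

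The second condition is false for all three tests, whatever v is. The first fails whenever v > T.

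**Values tried:** v = k x 1.01 x U, with k = 1, 1.5, 2, 3, 5.

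- WBC: 11.1, 16.7, 22.2, 33.3, 55.6. All exceed 2.5, so none is graded.
- Platelets: 454.5, 681.75, 909, 1363.5, 2272.5. All exceed 124.999, so none is graded.
- ANC: 7.6, 11.4, 15.2, 22.7, 37.9. All exceed 1.000, so none is graded.

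Result: 0 of 15 enter an abnormality table. If the second condition becomes *no grade in that direction and v outside the normal range*, 15 of 15 enter.

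The result does not depend on the choice of U. Any upper limit above T gives the same answer, so the assumed 7.5 for ANC could be any figure above 1.000.

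**Does another rule in SAP 5.2 close the gap?** The rule that low and high abnormalities count equally concerns normal-range flags, which the same section reserves for ungraded tests.

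**Are the data there?** Blood counts are drawn about two weeks after each dose, at Weeks 2, 14, 26 and 50 (Protocol 9.1.5). These draws fall inside the 28-day post-dose periods that SAP 5 tabulates.

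**Illustration of size.** The documents give no rate of high counts. At an assumed 1%, 5% or 10% of the 110 subjects in Group 2A, the number omitted would be 110 x 0.01 = 1.1, 110 x 0.05 = 5.5, or 110 x 0.10 = 11.

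**The case against.** **High values have other routes.** SAP 5.2 makes recording of clinically relevant laboratory values as adverse events mandatory, and Protocol 9.3 obliges the investigator to review results and record relevant changes. Both documents say that laboratory data will be summarised by type of test. This stands. A reader might infer that high counts vanish from the report, and the documents do not support that. A gross rise would probably be recorded as an adverse event. What is missing is the systematic view by regimen, chiefly of milder elevations that no one judges relevant. The summary by test is promised without naming any statistic.

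**The protocol may not demand more.** A reader might infer that Protocol 11.5 requires two parallel classifications. Attachment 1 says that normal ranges should be considered when grades are assigned, and SAP 5.2 does this by treating a gradable value within local limits as normal. On that reading the SAP does not contradict 11.5. The fair statement is that the SAP is narrower than the most natural reading.

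**The rule could be read by direction.** Two rows are named as decreases, so a programmer might treat a high WBC as a test without a grade. That is possible, but 5.2 and 5.2.1 speak of tests and nowhere of direction. The neutrophil share of leukocytes, if reported as its own test, would be ungraded and flagged both ways. That could show some neutrophilia, but not a high absolute count as such.

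**Entry limits are not safety endpoints.** True. They show that the protocol regards high WBC and platelets as outside the healthy range it wanted, and no more.

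**Wider readings.** A reader might extend the point to hemoglobin, or to values between the normal limit and Grade 1. The documents do not make that case. SAP 5.2 sends results in ungraded zones to the adjacent worse grade, which may cover some such values. Leaving out results milder than Grade 1 is how a toxicity scale ordinarily works, and nothing in the documents raises a concern about high hemoglobin.

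**It comes late.** SAP 1 says that the Week 72 analysis is done and will not be rerun, and the extension schedule has no blood counts. This stands, and it decides the form of the fix.

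**Conclusion.** The point holds in a narrow form. Followed as written, SAP 5.2 and 5.2.1 place no post-vaccination WBC, ANC or platelet value above the normal range in any laboratory abnormality table. Such values would appear only as adverse events if judged clinically relevant, or in general summaries by test.

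This rests on taking the wording at face value (the switch is by test) and on the grading tables having no high-side row for these counts, which they do not. It does not rest on a particular upper limit of normal. The number of subjects concerned cannot be derived from the documents.

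The weight is moderate. It is a reporting gap in a primary safety objective, caused by a stated rule and not just by missing detail. It does not show that a safety signal was missed.

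**What to change.** Amend SAP 5.2 and 5.2.1 so that the fallback works by test and direction. Suggested sense: *where a test has no toxicity grade in a given direction, the worst emergent abnormality against the laboratory normal range in that direction is tabulated by regimen and period; this applies at least to high WBC, ANC and platelets.*

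Because the main-study analysis is closed and the extension adds no counts, produce this as a supplementary main-study safety table, using the SAP's existing definitions of emergent and of the post-dose periods.

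The cost is one or two sentences in the SAP, one additional table run, and a few extra rows that will mostly show mild elevations. Grading against laboratory normal limits is already part of SAP 5.2, so no new data are needed. The table must carry a post hoc label, since it is specified after unblinding and after the Week 72 results.

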## 5.3. Vital Signs

### 5.3.1. Definitions

Vital sign measurements will be performed at the time points indicated in the Time and Events Schedule (see CTP). Following parameters will be summarized:

- Temperature (°C)
- Blood Pressure: systolic/diastolic (mmHg)
- Pulse rate (bpm)

For definition of emergent refer to section [5.2](#).

### 5.3.2. Analysis methodology

Any clinically relevant vital signs occurring from signing of the ICF onwards must be recorded on the adverse event page of the CRF and are analyzed as AEs. Tabulations of the parameters per period following vaccination will be provided. All findings will be listed by subject and by time point. Tabulations of the worst emerging abnormalities will be performed for parameters if applicable (see grading on [APPENDIX 1](#)).

Physical examination data will only be listed.

## 6. IMMUNOGENICITY

### 6.1. Analysis specifications

The analysis of immunogenicity will be done on the PPI analysis set (Section [2.3](#)).

### 6.2. Immune Response Parameters

Humoral and cellular immune responses as measured by the following immune assays will be analyzed:

#### Humoral response

- Env ELISA IgG-t gp140
- ELISA IgG 1-4
- TZM-BL
- ADCP gp140
- BAMA
- Ad26 VNA

#### Cellular response

- ELISpot
- ICS

### 6.3. Immune Response Analysis

No formal hypothesis on immunogenicity will be tested however at week 28 the differences between the 2 active groups (Ad26.Mos4.HIV + gp140/ Ad26.Mos.HIV + gp140) will be explored by means of a GMR including 95%CI and by a 2-sample t -test on the log data if those are normally distributed or by a Wilcoxon rank sum test otherwise. Those analyses will be performed on the following assays:

- ELISA: Clade C (C97ZA.012), Mos1
- ADCP: Clade C (C97ZA.012), Mos1
- ELISpot: Env peptide pool PTE, Gag peptide pool PTE, Pol peptide pool PTE

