3. STUDY DESIGN AND RATIONALE

3.1. Overview of Study Design

This is a randomized, double-blind, placebo-controlled, parallel, interventional, Phase 1/2a study in healthy HIV-uninfected adult men and women aged 18 through 50 years. A target of 198 subjects will participate in this study, randomized into one of 4 subgroups: 55 subjects will receive vaccination with Ad26.Mos.HIV and Clade C gp140 in Subgroup 1A, 11 subjects will receive placebo in Subgroup 1B, 110 subjects will receive vaccination with Ad26.Mos4.HIV and Clade C gp140 in subgroup 2A and 22 subjects will receive placebo in Subgroup 2B. Randomization will be stratified by region. Subjects will be enrolled regardless of their baseline Ad26 seropositivity. Subjects will receive study vaccine or placebo according to the time points in [Table 1](#).

The main study will be conducted in 3 phases: a 4-week screening period (with 2 extra weeks to allow for start of hormonal contraception for female subjects or female partners of male subjects); a 48-week vaccination period during which subjects will be vaccinated at baseline (Week 0) and Weeks 12, 24, and 48; and a follow-up period to the final main study visit at Week 72. An optional LTE phase (approximately 3 or 4 years after Week 72 depending on the length of follow-up which subjects consent to) will be performed for subjects randomized to Group 2A, who have received all 4 vaccinations and are negative for HIV infection at Week 72. The vaccination regimen of Group 2A (including Ad26.Mos4.HIV and Clade C gp140) forms the basis for the regimens that will likely be evaluated in future studies. The duration of the subject's participation will be approximately 76 weeks for subjects not participating in the optional LTE phase and approximately 220 or 268 weeks for subjects participating in the optional LTE phase (approximately 3 or 4 years after the end of the main study, respectively).

After vaccination, subjects will remain under observation at the study site for at least 30 minutes for presence of any acute reactions and solicited events. In addition, subjects will record solicited

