5. TREATMENT ALLOCATION AND BLINDING

Treatment Allocation

Procedures for Randomization

Central randomization will be implemented in this study. Subjects will be randomly assigned to one of 2 treatment groups and to one of 2 subgroups within each group based on a computer-generated randomization schedule prepared before the study by or under the supervision of the sponsor. The randomization will be evaluated by using randomly permuted blocks and stratified by region.

The interactive web response system (IWRS) will assign a unique treatment code, which will dictate the treatment assignment and matching study vaccine for the subject. The requestor must use his or her own user identification and personal identification number when contacting the IWRS, and will then give the relevant subject details to uniquely identify the subject.

Blinding

The subjects, study-site personnel (except for those with primary responsibility for study vaccine preparation and dispensing), and investigator will be blinded to study vaccine allocation until Week 72, with the exception of the partial unblinding for the start of the optional LTE phase (see below). The sponsor will be blinded to study vaccine allocation until the Week 28 analysis (see Section 11.6).

An interim immunogenicity analysis will be performed once approximately 60 subjects have completed the Week 16 visit and will be unblinded at the group level, but not at the subject level. Study-site personnel (except for those with primary responsibility for study vaccine preparation and dispensing), the sponsor (except for programming, statistics, clinical, and clinical immunology personnel involved in the analysis, and the sponsor committee involved in making future decisions for the program) and subjects will remain blinded to study vaccine allocation.

The pharmacist with primary responsibility for vaccine preparation (see Section 14.3) will not be blinded to the study vaccine. In order to preserve blinding, he/she will place an overlay on the syringes.

The investigator will not be provided with randomization codes. The codes will be maintained within the IWRS, which has the functionality to allow the investigator to break the blind for an individual subject.

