11.4. Immunogenicity Analyses

Descriptive statistics (actual values and changes from reference with 95% confidence interval) will be calculated for continuous parameters. Frequency tabulations will be calculated for discrete parameters. Graphical representations of changes in immunologic parameters will be made as applicable.

No formal hypothesis on immunogenicity will be tested. The analysis of immunogenicity will be done on the (per protocol) immunogenicity population as defined in Section [11.2](#).

Differences between groups at a specific time point will be tested for exploratory purposes by a 2-sample t-test if the data appear to be normally distributed. If not, the non-parametric Wilcoxon rank sum test will be used. If portions of the measurements are censored below the assay quantification limit, the Gehan-Wilcoxon test will be employed. All statistical tests will be 2-sided and will be considered statistically significant if $p<0.05$.

Frequency tabulations will be calculated for discrete (qualitative) immunologic parameters. Significant differences between groups will be determined by a 2-sided Fisher's exact test.

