## 1. INTRODUCTION

This statistical analysis plan (SAP) was initially written to describe the analyses of the main part of the study (up to Week 72). This updated version covers also the reporting of data collected till the end of the long-term extension (LTE) which lasted up to Week 264 (final analysis at end of study) for the group 2A receiving the full vaccination regimen ‘Ad26.Mos4.HIV/Ad26.Mos4.HIV + gp140’. At the time this SAP was written the Week 72 statistical analysis was already performed and will not be rerun. The below described analyses will be performed on fully unblinded data.

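### Randomisation is stratified by region, but the exploratory Week 28 regimen comparison ignores region; if region predicts response, its 95% CI is wider than necessary and its test is conservative

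*SAP*

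**What the plan says.** Protocol 3.1 states: "Randomization will be stratified by region". Protocol 5 gives the method: "The randomization will be evaluated by using randomly permuted blocks and stratified by region". Region is the only stratification factor named.

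SAP 6.3 compares the two active regimens at Week 28. The estimate is a geometric mean ratio with its 95% interval. The regimens are also tested, "by a 2-sample t -test on the log data if those are normally distributed or by a Wilcoxon rank sum test otherwise". This applies to seven measures: ELISA and ADCP, each for Clade C (C97ZA.012) and Mos1, and ELISpot for the Env, Gag and Pol PTE pools. Protocol 11.4 names the same tests ("Differences between groups at a specific time point will be tested for exploratory purposes by a 2-sample t-test"), adds a Gehan-Wilcoxon test for censored data, and sets the level: "All statistical tests will be 2-sided and will be considered statistically significant" at p<0.05. Neither document has a region term or a stratified version of any of these tests.

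Both documents give the comparison exploratory status; SAP 6.3 opens with "No formal hypothesis on immunogenicity will be tested".

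Geography appears elsewhere in the SAP in three places. Section 4.1 lists region and country as separate baseline characteristics. Section 2.4 defines a country subgroup (Rwanda, USA), which section 6.3 uses for graphs. Section 2.2 plans no pooling of centres and points to that subgroup.

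**The concern.** When allocation is balanced within region, a difference in response between regions largely cancels out of the regimen contrast, so the true sampling variance of that contrast contains only within-region variance. The two-sample t-test and its CI estimate their standard error from the total variance, which still includes the between-region part. The reported standard error is then too large, the 95% CI covers more than 95% of the time, and a real difference between the trivalent and tetravalent regimens is more likely to be missed. The rank sum test behaves in the same way.

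Only precision is at stake. It matters to the extent that this GMR will be read as the comparison of the two regimens: Env-binding antibody is a primary endpoint, and Protocol 11.3 uses a 1.5-fold difference in it to describe what the sample size can detect.

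**Working it through.** **Inputs from the documents.** Protocol 11.3: about 100 (2A) versus 50 (1A) evaluable subjects, SD s = 0.4 on log10, 1.5-fold difference (log10 1.5 = 0.176), 1-sided 5%, 80% power. Protocol 11.4: 2-sided 5% for the analysis. SAP Definition of Terms: 5:1:10:2 allocation.

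**Assumptions.** The documents give no region effect, no number of strata and no split. I assume two regions, with share p of subjects in one of them and a difference d (log10) between them, and hold the total SD at 0.4.

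**Step 1: reproduce the plan's figure.** SE = 0.4 × √(1/100 + 1/50) = 0.0693, and 0.176/0.0693 = 2.54. One-sided power = Φ(2.54 − 1.645) = 0.815 (0.812 with the noncentral t), which agrees with the stated 80%. At the two-sided 5% level used in the analysis, power = Φ(2.54 − 1.96) = 0.72 (0.714 with the noncentral t). This is the starting point for the power figures below.

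**Step 2: effect of ignoring region.** The share of variance explained by region is R² = p(1 − p)d²/s². The true SE of the regimen difference is √(1 − R²) times the SE that the unadjusted analysis uses. Hence:
- CI width, adjusted over unadjusted: √(1 − R²)
- actual two-sided type I error, unadjusted: 2[1 − Φ(1.96/√(1 − R²))]
- unadjusted CI on the GMR scale: estimate ×/÷ 10^(1.976 × 0.0693) = 1.37, where 1.976 is the t quantile on 148 df

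Example for p = 0.5, d = 0.4: R² = 0.25 × 0.16/0.16 = 0.25; √0.75 = 0.866; type I error 2[1 − Φ(2.263)] = 0.024; adjusted GMR factor 10^(0.1369 × 0.866) = 1.31.

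**Step 3: results for p = 0.5.** R² comes from the formula. Width ratio, type I error and power come from a simulation of 200,000 trials per row.

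| d (fold) | R² | CI width ratio | Type I error, unadjusted | Power for 1.5-fold, unadjusted → adjusted | Adjusted GMR factor (unadjusted 1.37) |
|---|---|---|---|---|---|
| 0 (1.0) | 0 | 1.000 | 0.051 | 0.715 → 0.715 | 1.37 |
| 0.1 (1.26) | 0.016 | 0.992 | 0.049 | 0.716 → 0.721 | 1.37 |
| 0.2 (1.6) | 0.063 | 0.968 | 0.043 | 0.718 → 0.739 | 1.36 |
| 0.3 (2.0) | 0.141 | 0.926 | 0.034 | 0.726 → 0.777 | 1.34 |
| 0.4 (2.5) | 0.25 | 0.865 | 0.023 | 0.741 → 0.830 | 1.31 |

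Coverage of the unadjusted CI is one minus the type I error, so it rises from about 95% to 97.7%. Adjusted type I error stays at 0.050 to 0.051. The formula gives width ratios of 1.000, 0.992, 0.968, 0.927 and 0.866, in agreement with the simulation.

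**Step 4: sensitivity.**
- With a 30:70 split the width ratios are 1.000, 0.993, 0.973, 0.938 and 0.888.
- For the rank tests (60,000 trials, p = 0.5, normal data), Wilcoxon power is 0.695, 0.691, 0.698, 0.707 and 0.710, against 0.691, 0.695, 0.718, 0.757 and 0.812 for van Elteren.
- A separate simulation used permuted blocks of 18 (an assumed block size, the sum of 5:1:10:2) and 10% random dropout, so that within-region balance was not exact. At R² = 0.2, unadjusted type I error was 0.028 to 0.031, and power was 0.73 unadjusted against 0.80 adjusted. The conclusion is unchanged.

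**The case against.** The strongest case against is that no harm is shown from the documents themselves. The planned analysis is valid and errs on the conservative side. A simple unadjusted contrast is defensible in a Phase 1/2a trial with no formal hypothesis, and no decision rule depends on the p-value. The visible gains need large regional effects: up to a 1.6-fold difference, already more than the 1.5-fold regimen effect used for planning, the interval narrows by only 3%. The 14% figure needs a regional shift equal to the whole assumed SD. That SD is given only for Env-binding titers, not for ADCP or ELISpot. The SAP also plans country graphs for five of the seven measures, which would show whether geography matters. Finally, "At the time this SAP was written the Week 72 statistical analysis was already performed and will not be rerun", and SAP v2.0 was written to add extension data from Group 2A alone, so little remains to change.

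Most of this stands, and it limits the weight of the point without removing it. The country graphs do not adjust the GMR, its CI or the test. The documents give no reason to assume that the region effect is nil. The late timing rules out pre-specification but not a supplementary analysis. It is also fair that the levels of region are never defined and that two regions are an assumption: the two countries in SAP 2.4 are consistent with it but do not establish it. Exclusions from the per-protocol immunogenicity set could weaken the within-region balance slightly; only random dropout was examined.

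**Conclusion.** The point holds as a minor matter of efficiency. The design stratifies by region and the Week 28 regimen comparison does not use it. The direction follows from the design and is not in doubt: if region predicts response, the CI over-covers and the test is conservative. The GMR is not biased, type I error is not inflated and the stated power is not undermined.

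The size cannot be fixed from the documents. Under the assumptions above it runs from nothing, through about 3% of CI width at a 1.6-fold regional difference, to about 14% at 2.5-fold (11% with a 30:70 split). The likely practical effect is small unless regional differences are large. The change is worth considering because it costs almost nothing; it is not a reason to doubt the planned result.

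**What to change.** Add one paragraph to SAP 6.3 for a supplementary Week 28 analysis:

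- Estimate the GMR and 95% CI from a linear model on log10 response with terms for regimen and region.
- Where the normality condition leads to the Wilcoxon test (possibly for ELISpot), use its region-stratified van Elteren version.
- Define region as the stratum used at randomisation and list its levels, since SAP 4.1 treats region and country as different variables.
- Keep the planned unadjusted results as reported. State that the supplementary analysis was added after unblinding and does not replace them.

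The cost is that paragraph and a short program on existing data. With two regions the model uses one of the 148 degrees of freedom; more regions would use correspondingly more. The Week 72 analysis need not be rerun.
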